6.2 ALTERNATIVE TREATMENTS

The alternative treatments for the subjects participating in this investigation are to continue their medical care under the direction of their primary physicians.

6.3 POTENTIAL BENEFITS

There may be no direct medical benefit to subjects in the study. It is hoped that researchers will learn more about the effectiveness of using oral NO₂ to improve strength, gait speed and balance. Oral NO₂ may also increase efficiency of work by reducing their oxygen uptake required for the same work intensity. We hope the information learned from this study will benefit other heart failure patients in the future.

6.4 DATA SAFETY MONITORING

6.4.1 Data Safety Monitoring Board (Safety Officer)

In lieu of a Data Safety Monitoring Board, the funding agency, the National Institute on Aging, (NIA) has approved the use of a Safety Officer for this small sample, Phase II trial. [name] has appointed [name], UPMC Shadyside-Cardiology as the Safety Officer. The NIA has approved the appointment. The PI will provide [name] a detailed written summary of all adverse events on a monthly basis; any that are serious, unexpected, and potentially treatment-related adverse events (SAEs) will be immediately (within 24 hours) reported to the Human Research Protection Office, the Safety Officer, NIA Program Officer, and the Sponsor. In the monthly SO report, we will compare and contrast any SAE with prior events (or more frequently as indicated). [name] will review accumulating data from research activities to assure the continued safety of human subjects, relevance and appropriateness of the study, and the integrity of research data.

See also sections 6.4.5 and 6.4.6 regarding reporting of SAEs and/or fatalities.

To remain objective, [name] will maintain independent from the study. Accordingly, he will not be directly involved in the conduct of the study and will not have scientific, proprietary, financial or other interests that may affect independent decision-making. Signed documents confirming no conflict of interest will be provided with the application for approval to the NIA and maintained in the study regulatory binder.

In addition, the report to [name] will address the following information as it is submitted to the University Of Pittsburgh Human Research Protection Office (HRPO) at the time of annual review or more often as required:

- A list of the research personnel who participated in the data and safety monitoring.
- The frequency of monitoring that took place during the renewal intervals and/or the dates that data and safety monitoring was conducted.
- A summary of cumulative data related to unanticipated problems (including adverse events) including a determination of causality and whether the risk to benefit assessment has changed.
- If appropriate, a summary of pertinent scientific literature reports, therapeutic developments, or results of related studies that may have an impact on the safety of study participants or the ethics of the research study.
- A summary of the outcome of reviews conducted to ensure subject privacy and research data confidentiality.
- Final conclusions regarding changes to the anticipated benefit-to-risk assessment of the study

participation and final recommendations related to continuing, changing, or terminating the study.

6.4.2 Data Safety Monitoring Plan

Monitoring of safety and data quality in the proposed study will be the responsibility of all personnel on the project, with primary responsibility and supervision by the PI. The University of Pittsburgh HRPO will approve the informed consent document for the study and provide institutional oversight of data and safety issues. The study protocol will be approved prior to recruiting or obtaining consent from any participants. Moreover, the study will be reviewed at a minimum of an annual basis by the HRPO committee. Each participant will sign the informed consent document described above prior to participating in the study. To ensure participant safety, once participants are enrolled in the study, study staff will immediately report all adverse and serious adverse events to one of the physician investigators or PI. The PI will, per standardized procedures, report serious adverse events to the HRPO, Safety Officer, FDA, and NIA Program Officer for their review and to the sponsor as indicated. With regard to monitoring of data quality and protected health information, all required personnel proposed for this project will have the required human subjects and confidentiality training, which includes information about maintaining data integrity and security. Confidentiality will be guarded using established procedures such as double locked files and facilities for storing research charts, coding by study identification numbers rather than any personally identifying information to avoid revealing the identity of subjects, and aggregating data across participants. The key linking names and study identification numbers will be kept separately from the data sets with limited access by study personnel. Only study personnel will have access to the data sets on protected servers. In order to maintain the highest standard of data entry quality, all data will be double-entered, with discrepancies highlighted so that they can be reviewed by the project coordinator. Oversight of all aspects of data management will occur by the PI.

Data Monitoring Plan. The proposed study will use the FDA definition of adverse events (AE) and serious adverse events (SAE). Any SAE, which is unexpected and related to study intervention, will be reported immediately to the HRPO, Safety Officer, FDA, and NIA Program Officer and will be followed by an additional letter detailing the nature of the SAE. In the event that a participant either withdraws from the study or the investigators decide to discontinue a participant due to a SAE, the participant will be monitored by the PI physician investigator until (a) a resolution is reached (e.g., the problem has resolved or stabilized with no further change expected), (b) the SAE is determined to be clearly unrelated to the study intervention, or (c) the SAE results in death. Outcomes of SAEs will be regularly reported to the HRPO and the sponsor. A summary of the SAEs that occurred during the previous year will be included in the annual progress report as well as in the annual HRPO renewal.

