1. While the standardized breakfast is being prepared, interval history/AEs and temperature, RR, BP, HR, SpO₂, MetHb, body weight, and symptom assessment will be collected. A brief physical exam will be completed. The Canadian Clinical Frailty Scale will be repeated.
2. Medication compliance via drug diary cards, empty pill box compartments, and subject report will be assessed. Unused capsules will be counted and returned to IDS following the visit.
3. The 3DFR issued at Visit 5 will be reviewed with the subject for clarification and completion.
4. ActiGraph and diary will be collected if not at previous visit
5. Blood draw to include: Inflammatory peptides (IL-1, IL-6, IL-15, TNFα), adipokines (leptin, adiponectin). GFR, BNP or NT-pro BNP, platelet sample and NO₂ levels. Additional NO₂ levels will be drawn at 30 minutes, 60 minutes and 120 minutes. Total volume of blood drawn will be about 64 ml (about 4.3 tablespoons). If subjects have had BNP or GFR within approximately the last month via their clinical care, the study physician can defer this blood draw.
6. Skeletal Muscle Biopsies: same as described in Visit 3.
7. Transthoracic Echocardiogram. The subject may be transported to a UPMC Presbyterian/Montefiore lab for an echocardiogram.

Following the echocardiogram subjects will be discharged. They will receive payment for visits 5-7 and study drug period.

End of Trial and Follow-Up Period

Post Study drug/placebo Telephone Assessment (about 7 days following Visit 7)

- Telephone assessment for interval histories, muscle biopsy follow up and AEs will be completed. Any remaining symptoms or AEs which are suspected to be related to the study drug/placebo will be evaluated by [name] and follow-up plan for care devised as needed.

Table.2.2.1 Study Visits and Assessments		
Phase	Visit	Assessments and Procedures
Screening	Visit 1	Informed consent and physical exam; Hgb* Home accelerometry; Echo†; issue 3DFR, frailty assessment
Pre- Assessment Series	Visit 2 (within 28 days of Visit 1)	Non-invasive functional assessment battery: Symptom-limited nCPET; Fatigability assessments (perceived [SS] and performance [6MWT]), NIRS during nCPET, SS, 6MWT, Accelerometry during nCPET, SS, 6MWT and 1 week at home with diary; Hand grip, SPPB, Questionnaires
	Visit 3A (5 days ±2 days from V2)	³¹ P MRS protocol; review 3DFR and return ActiGraph 3A or 3B per dates; pre-cath bloodwork if applicable

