2.5.3 Efficacy Analysis

Overview-We will use SAS[®] version 9.3 (SAS Institute, Inc., Cary, North Carolina) for all analyses. The main focus of the analyses of the present pilot study will be to establish feasibility and obtain preliminary findings, and descriptive statistics needed for formal sample size and power computations for a subsequent larger randomized trial to be proposed under the R01 mechanism to obtain more definitive conclusions. Therefore, we will pay greater attention to magnitudes of effects rather than statistical significance alone, and similar to published pilot studies in other settings, also employ graphical methods such as needle plots that focus on change at the individual level rather than on average^{87, 88}. First, we evaluate the distributional characteristics of the data set, the prevalence of missing values and general data quality using appropriate descriptive statistics and graphical summarizations for all variables for each arm for each time point, as well as baseline to follow-up change scores. Second, the baseline measures and participant characteristics will be compared between the two arms using differences in magnitudes of the descriptive statistics, and independent samples *t*-, Wilcoxon rank sum, Kruskal-Wallis, chi-square or Fisher's exact tests, as appropriate. Any variables found to be meaningfully different will be noted when interpreting the findings. Third, main analyses below will be performed.

Aim 1-We will conduct Aim 1 analysis on an intention-to-treat basis. We will fit a series of linear mixed models using the SAS[®] MIXED procedure with baseline to follow-up change in primary outcome RPE, secondary outcome peak VO₂, and each of the other secondary outcomes as the

dependent variable; and treatment (NO₂/placebo), follow-up time (4 weeks) and their interaction as main factors of interest; baseline value of the dependent variable as the sole and a catch-all covariate; and a subject random effect to account for multiple follow-up measurements from each participant. We will construct appropriate means contrasts to compare the treatment groups at each of the follow-up time points. The magnitudes of the estimated means contrasts and graphical displays of individual change will be considered to support Aim 1 hypotheses rather than and in addition to statistical significance at the 0.05 level.

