2.5.4 Safety Analysis

We will describe and descriptively compare proportions of those with clinical endpoints/adverse events such as hospitalizations, urgent clinic/ER visits, and death between the treatment groups, as using chi-square and Fisher's exact tests for dichotomous outcomes with such a small number of participants is unlikely to reliably demonstrate statistical significance.

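### A participant who leaves because of a serious adverse event has no common safety follow-up date, and a judgement of unrelatedness is one of three ways monitoring can end

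*Combined protocol and SAP*

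**What the plan says.** The data monitoring paragraph of section 6.4.2 covers a participant who withdraws, or whom the investigators discontinue, because of an SAE. For that person, "the participant will be monitored by the PI physician investigator until" one of three conditions is met:

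- (a) the event has cleared up, or is stable and not likely to alter;
- (b) "the SAE is determined to be clearly unrelated to the study intervention"; or
- (c) the participant dies of the event.

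The safety analysis in section 2.5.4 is, descriptively, to "compare proportions of those with clinical endpoints/adverse events such as hospitalizations, urgent clinic/ER visits, and death between the treatment groups". It gives no restriction to related events, no start or end date for counting, and no person-time denominator. Section 2.5.3 states "We will conduct Aim 1 analysis on an intention-to-treat basis"; no analysis population is named for safety.

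For those who reach the end of the trial, section 2.2 gives the last contact as the "Post Study drug/placebo Telephone Assessment (about 7 days following Visit 7". The weekly calls in the same section belong to the dosing period. Section 6.4.7 discontinues participation after certain adverse events and schedules no later safety contact.

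Section 6.4.2 adopts the FDA definition of an SAE. Section 6.4.5 counts an event as an SAE only if the PI thinks it study-related.

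**The concern.** The comparison in 2.5.4 reads as all-cause: it names hospitalizations, urgent visits and death, and does not filter them by relatedness. Such a comparison needs the same observation period in both arms. For participants who leave because of an SAE, the plan sets no calendar end. Under (a), monitoring may stop at resolution, well before a completer's closing call. Under (b), it may stop while the event is still unresolved, because someone has judged the cause. A later death, a first hospitalization or a first urgent visit in that participant need not then be captured. An attribution of clear unrelatedness also cannot be revised in the light of a later course that nobody observed.

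The participants affected are likely to be among the sickest in the trial. The pilot's descriptive statistics are meant to inform a larger trial (2.5.1, 2.5.3), so incomplete event counts would be carried forward.

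**Working it through.** **Inputs.** Visit 5 at 28 ±3 days from Visit 4, which is the first dose; Visit 6A 5 ±2 days after Visit 5; Visit 7 either 10 ±4 days after 6A, or 5 ±2 days after 6B with 6B itself 5 ±2 days after 6A (section 2.2 and its visit table). Closing call about 7 days after Visit 7 (2.2). Stated maximum time on drug or placebo 52 days (2.3.3). Nine participants per arm (Planned Sample Size).

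**1. Reproduce the plan's figure.**
- Maximum without 6B: 31 + 7 + 14 = 52 days.
- Maximum with 6B: 31 + 7 + 7 + 7 = 52 days.

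The stated 52 days reproduces on both routes.

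**2. Observation window for completers.**
- Minimum day of Visit 7: 25 + 3 + 6 = 34 without 6B, or 25 + 3 + 3 + 3 = 34 with it.
- Closing call: 34 + 7 = 41 to 52 + 7 = 59 days from first dose.
- At the target intervals: 28 + 5 + 10 + 7 = 50 without 6B, and 28 + 5 + 5 + 5 + 7 = 50 with it.

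**3. Window for a participant who leaves because of an SAE.** The documents give no figure. As an assumption for illustration, suppose monitoring ends on day 12. The time unobserved, relative to a completer, is 41 − 12 = 29 to 59 − 12 = 47 days.

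**4. Effect of one missed event.** The measure in 2.5.4 is the proportion of participants with each type of event.
- A first event of a type not yet recorded for that participant: 1/9 = 11.1 percentage points.
- A readmission in someone already counted as hospitalized: 0 points on the hospitalization proportion.

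**5. How likely a missed event is.** The documents give no event rate. Assume a constant hazard, a probability p of an event by day 45, and monitoring that ends on day w. For a participant without that event by day w, the risk left unobserved is 1 − (1 − p)^((45 − w)/45).

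| p by day 45 | w = 14 | w = 28 |
|---|---|---|
| 10% | 7.0% | 3.9% |
| 20% | 14.2% | 8.1% |
| 30% | 21.8% | 12.6% |

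These are illustrations on assumed values, per affected participant.

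**6. Reach of condition (b).** Under the definition in 6.4.2, an SAE may be unrelated and (b) has something to act on. Under 6.4.5, an event the PI does not think study-related is not an SAE. Condition (b) then has little to act on, and a participant who leaves after an unrelated serious event may fall outside the monitoring rule altogether. The two sections give the rule different scope.

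**The case against.** The case against giving this weight is substantial, and much of it stands.

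- **The rule is not simply to monitor until the event is called unrelated.** A reader might infer that from (b) alone. Section 6.4.2 gives three alternatives, and the threshold in (b) is clear unrelatedness. An event that does not meet it is followed to resolution, stabilisation or death.
- **Condition (b) is not the main cause.** Condition (a) also ends monitoring before a completer's call. Deleting (b) alone would leave most of the gap, which is the lack of a common end date.
- **The documents do not order event collection to stop.** They are silent on collection after monitoring ends, and 6.4.2 says SAE outcomes will be reported regularly. What stands against this is that no contact is scheduled through which a later event would become known.
- **Bias between arms is a narrow possibility.** A reader might infer that unblinding makes attribution, and so follow-up, differ by arm. The listed triggers in 2.3.3 and 2.3.5 are methemoglobin above 5%, hypotension with related symptoms, and suspected product-related events. These are suspected drug effects and unlikely candidates for clear unrelatedness. An independent Safety Officer also receives monthly summaries of all adverse events, and causality is part of the reporting (6.4.1). The documents do not show that observation time will differ by arm.
- **The trial is small and the analysis descriptive.** Section 2.5.4 does not rely on tests, and no conclusion of the pilot is shown to depend on this rule.

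**Conclusion.** The point holds as a gap in follow-up, of minor importance. For participants who leave because of an SAE, observation of hospitalizations, urgent visits and deaths can be shorter than the 41 to 59 days given to completers, and its length can depend partly on a causality opinion. The analysis in 2.5.4 makes no allowance for this.

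The size is 11.1 percentage points in one arm for each missed first event of a new type. It would be wrong to apply that figure to any readmission. How many participants would be affected cannot be estimated from the documents; the number may well be zero or one.

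The conclusion rests on two readings: that 2.5.4 means events of any cause, since it states no filter, and that no unscheduled contact would bring later events to light. The SAE definitions in 6.4.2 and 6.4.5 conflict on any reading.

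**What to change.** 1. **Section 6.4.2.** Keep recording relatedness, but do not let it end safety data collection. For every dosed participant who has not withdrawn consent to contact, collect vital status, hospitalizations, urgent visits and SAE outcome. Continue to the later of (i) resolution or stabilisation of the SAE and (ii) the date on which that participant's call after Visit 7 would have fallen. Use the booked Visit 7 date plus 7 days; if none was booked, the target intervals give day 50 from first dose on either route.
2. **Section 2.5.4.** Count events only within the window ending on that call date, in both arms and whatever the attribution. Information gathered later on an unresolved SAE is reported but not counted in the comparison.
3. **Sections 6.4.2 and 6.4.5.** Reconcile the two SAE definitions so that it is clear whom the follow-up rule covers.

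The cost is a short amendment to these three sections and a few telephone calls by existing staff for the few participants likely to be affected. The change concerns data collection only and leaves dosing and clinical care as they are.

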6.4.3 Parameters to be monitored

The following progress will be monitored throughout the course of the research to ensure the safety of subjects as well as the integrity and confidentiality of their data.

- An evaluation of the progress of the research study, including subject recruitment and retention, and an assessment of the timeliness and quality of the data.
- A review of collected data (including adverse events, unanticipated problems, and subject withdrawals) to determine whether there is a change to the anticipated

benefit-to-risk assessment of study participation and whether the study should continue as originally designed, should be changed, or should be terminated.

- An assessment of external factors or relevant information (e.g. pertinent scientific literature reports or therapeutic development, results of related studies) that may have an impact on the safety and study participants or the ethics of the research study.
- A review of study procedures designed to protect the privacy of the research subjects and the confidentiality of their research data.

The severity of adverse changes in physical signs or symptoms will be classified as follows:

- Grade 1 (Mild): asymptomatic or mild symptoms; clinical or diagnostic observation only; intervention not indicated.
- Grade 2 (Moderate): minimal, local or noninvasive intervention indicated; limiting age-appropriate ADL (Activities of Daily Living).
- Grade 3 (Severe): medically significant but not immediately life-threatening; hospitalization or prolongation of hospitalization indicated; disabling; limiting self-care ADL.
- Grade 4 (Life-threatening): consequences; urgent intervention indicated.
- Grade 5 (Death): event is a direct cause of death.

6.4.4 Frequency of Monitoring

[name] will review subject safety data as it is generated. [name] and the research staff will meet at least bi-weekly to re-evaluate study goals, subject recruitment, data coding and retention, documentation and identification of adverse events, complaints and confidentiality of subjects. There will be an evaluation of the progress of the research study, including assessments of data quality, time lines, participant recruitment, accrual, and retention. [name] will also review the outcome and adverse event data to determine whether there is any change to the anticipated benefit-to-risk ratio of study participation and whether the study should continue as originally designed or should it be re-evaluated and changed. [name] will meet with the entire investigatory team at regular intervals for broader discussion of relevant details. Simultaneously, the Safety Officer will receive monthly reports of all AEs as described in section 6.4.1.

6.4.5 Reportable Adverse Event

For this study, a serious adverse event is any untoward clinical event that is thought by [name], PI, to be study-related, and results in any of the following outcomes:

1. Death
2. A life threatening adverse event
3. Inpatient hospitalization or prolongation of an existing hospitalization

4. A persistent or significant incapacity or substantial disruption of the ability to conduct normal life functions
5. A congenital anomaly or birth defect
6. Important medical events (that may not result in death, be life threatening, or require hospitalization) may be considered serious when, based upon appropriate medical judgment, they may jeopardize the patient, or subject, and may require medical, or surgical intervention to prevent one of the serious outcomes listed above.

If clinically important and unexpected adverse experiences or clinically important study-related adverse experiences occur, they will be recorded on the adverse event case report form.

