Subjects will receive sufficient study drug/placebo supply to cover the period up to the next scheduled visit at Visit 5 and/or through Visit 7 as needed. We will instruct subjects to return all of the study drug packaging, including unused study drug and empty packaging at each study visit and/or at the time of discontinuation from treatment.

Study staff will review medication administration and use of the drug diary card with all subjects. Subjects will be asked to record the time they take the drug each day and any symptoms with severity rating and/or health events during the dosing period.

The study staff and/or CTRC RN will review biopsy site care with subjects and if indicated, remind subjects to resume their normal anti-coagulation/anti-platelet/anti-diabetic medications.

The subject will receive payment for visits 1-4 and can then be discharged.

Drug Dosing Period and Outpatient Monitoring

Subjects will then complete no less than 28 (-3) days on drug. Subjects will continue on drug/placebo through the post testing period; the duration will vary with the visit windows and if subjects are doing both 6A and 6B. During the 28-day period, subjects will be called on a weekly basis by study staff, beginning on the visit 4 day plus 7 days \pm 2 days, and continuing approximately weekly thereafter. Study staff will query subjects on any symptoms, home BP readings if applicable, health care, including medication changes, or adverse events, and compliance with study drug/placebo regimen. Any AEs or medical issues of concern will be promptly communicated to the PI or covering study physician by email or phone depending on urgency; and AEs will be documented in the study log which is reviewed with PI at least bi-

weekly. Subjects will be again reminded to communicate any medication changes prescribed by their health care team to study staff as soon as possible, not to wait for the weekly call. (Serious adverse events will be reported as described in Section 6.4.5.) Management of hypotension or methemoglobinemia related symptomatology will be as described in 2.3.3 Dose Selection, subsection Dose Reduction.

Post Assessments (continuing on NO₂/placebo tid)

Visit 5

This visit will be scheduled 28 ±3 days from Visit 4, take place in the UPMC Montefiore EMRC and/or Pepper SMART Center and include all of the Functional testing described in Visit 2.

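### Section 6.4.5 makes the PI's view of study-relatedness part of the SAE definition, contradicting 6.4.2; if followed, serious events judged unrelated drop out of the routine SAE reports

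*Combined protocol and SAP*

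**What the plan says.** Section 6.4.5 gives the study's own definition: "a serious adverse event is any untoward clinical event that is thought by [name], PI, to be study-related". The sentence goes on to require one of six outcomes, among them inpatient hospitalization. The two requirements are joined by an and, so both must be met.

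Section 2.2, under the drug dosing period, points staff to that definition: "Serious adverse events will be reported as described in Section 6.4.5". Section 6.4.1 also refers the reader to 6.4.5 and 6.4.6 on SAE reporting.

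Section 6.4.2 says something different: "The proposed study will use the FDA definition of adverse events (AE) and serious adverse events (SAE"). It then uses relatedness as a further condition on events that are already SAEs. Its expedited rule reads "Any SAE, which is unexpected and related to study intervention, will be reported immediately". One of its end-points for follow-up is that "the SAE is determined to be clearly unrelated to the study intervention".

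Two routine outputs in 6.4.2 are stated for SAEs without any relatedness condition: "Outcomes of SAEs will be regularly reported to the HRPO and the sponsor" and "A summary of the SAEs that occurred during the previous year will be included in the annual progress report".

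**The concern.** Seriousness describes the outcome of an event. Relatedness is a judgment about its cause. Section 6.4.5 merges them, so one person's causal opinion decides whether a serious event is counted as an SAE at all, before relatedness has been recorded as a judgment that others can examine.

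Attribution in a single patient will be uncertain here. Participants are at least 70 years old and have heart failure, which can itself lead to hospitalization. Section 6.1.1 lists hypotension as frequent in heart failure subjects on higher nitrite doses, and Section 6.4.7 describes certain side effects as idiosyncratic in this population. Study personnel involved in assessments are blinded (Section 2.3.4), so attribution will normally be made without knowing the arm. With 18 subjects, review that keeps the events judged unrelated is one of the few ways a misattributed event might be noticed. Under 6.4.5 the SAE outcome reports and yearly summaries would omit exactly those events.

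**Working it through.** No arithmetic beyond a count applies. The check compares the definitions and then traces one test event through every reporting route.

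**Do the definitions conflict?**

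- Under 6.4.5, an SAE is an event with a listed outcome that the PI also thinks is study-related.
- Under 6.4.2, an SAE follows the FDA definition. The protocol does not reproduce that definition, so the comparison rests on how 6.4.2 uses the term.
- The expedited rule in 6.4.2 selects SAEs that are unexpected and related. If every SAE were related by definition, the second condition would do nothing.
- Section 6.4.2 also provides for an SAE found to be clearly unrelated. Under 6.4.5 an event the PI thinks unrelated never becomes an SAE.

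Section 6.4.1 puts the abbreviation for SAEs after a description of serious, unexpected and potentially treatment-related events. That is read here as a loose label on the 24-hour trigger and not counted as a separate definition.

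**Test event:** an inpatient hospitalization that the PI attributes to underlying heart failure.

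| Output | Section | Own relatedness condition? | 6.4.2 definition | 6.4.5 definition |
|---|---|---|---|---|
| SAE outcomes to HRPO and sponsor | 6.4.2 | No | Included | Omitted |
| Annual SAE summary | 6.4.2 | No | Included | Omitted |
| SAE comparison in monthly Safety Officer report | 6.4.1 | No | Included | Omitted |
| PI's general SAE reports | 6.4.2 | No | Included | Omitted on a plain reading |
| 24-hour report | 6.4.1 | Yes | Unchanged | Unchanged |
| Immediate report | 6.4.2 | Yes | Unchanged | Unchanged |
| Serious and unexpected events to HRPO | 6.4.6 | Yes | Unchanged | Unchanged |
| Study log | 2.2 | No | Included | Included |
| Monthly summary of all AEs to Safety Officer | 6.4.1, 6.4.4 | No | Included | Included |
| Adverse event data with causality, HRPO annual review | 6.4.1 | No | Included | Included |

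Count under 6.4.5: 3 routine outputs lost, or 3 + 1 = 4 with the general SAE reports; 3 routes retained; 3 expedited routes unchanged because each has its own relatedness condition. The 7-day FDA notification in 6.4.6 concerns fatal or life-threatening events and does not use the term SAE.

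**Follow-up.** Section 6.4.2 applies where a participant withdraws or "the investigators decide to discontinue a participant due to a SAE, the participant will be monitored by the PI physician investigator until" one of three end-points is reached. One end-point is that the event is clearly unrelated. Following 6.4.5 therefore costs follow-up only for a participant who leaves because of an event that is thought unrelated but has not been shown to be clearly so.

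**Case report form.** The closing sentence of 6.4.5 requires the adverse event form only for clinically important events that are unexpected or study-related. A hospitalization judged expected and unrelated need not be on that form either.

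**The case against.** The strongest reply has four parts.

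1. *The sections can be reconciled.* An event might first be thought related, become an SAE under 6.4.5, and later be found clearly unrelated, which would fit the follow-up rule in 6.4.2. This is a possible reading of that one phrase. It leaves the relatedness condition in the 6.4.2 expedited rule redundant, and it does not explain why 6.4.2 adopts a different definition.

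2. *Section 6.4.5 may be as loosely worded as 6.4.1.* Its heading concerns reportable events, and it could have been meant as a reporting trigger. However, it opens by saying what an SAE is for this study and lists the qualifying outcomes, and two other sections send the reader to it. What stands is that the protocol does not say which section prevails, so the consequence is conditional on 6.4.5 being followed.

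3. *Little is lost.* The Safety Officer sees all adverse events monthly, and the HRPO receives cumulative adverse event data with causality each year. For those two recipients the loss is mainly the SAE label. Section 6.4.3 grades severity whatever the cause, and Section 2.5.4 describes hospitalizations by arm with no relatedness condition. All of this stands and limits the severity. But Section 6.4 names no corresponding report of all adverse events to the sponsor, the FDA or the NIA Program Officer. Section 2.5.4 is an analysis by arm and not an oversight report, and the case report form rule may thin the data behind it.

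4. *The cited side effects point towards the drug.* Frequent hypotension and idiosyncratic intolerance might make the PI more ready to suspect nitrite, and no difference in misattribution between arms is shown. That is fair. The point claims no bias between arms, only that individual attribution is uncertain and should not decide whether an event is counted.

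**Conclusion.** The concern holds. Sections 6.4.2 and 6.4.5 give incompatible rules for what an SAE is, and the same hospitalization is or is not an SAE depending on which section staff read.

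If 6.4.5 is followed, a serious event the PI judges unrelated leaves three routine SAE outputs, or four on a plain reading of the general reporting sentence in 6.4.2. Three monitoring routes still carry it, and expedited reporting is largely unaffected. This is a contradictory reporting rule, not loss of the event. It should be fixed, but it does not threaten the trial.

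The conclusion rests on two readings: that 6.4.5 governs in practice, which its wording and the cross-references support, and that the SAE label in 6.4.1 is loose. If that label were a definition, the monthly SAE comparison would already be restricted under 6.4.1, and three sections would disagree instead of two. The documents give no rate of serious events, so the number affected cannot be estimated.

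**What to change.** - Delete the clause in 6.4.5 that makes the PI's view of study-relatedness part of the SAE definition.
- Use the single definition named in 6.4.2 throughout 6.4.1, 6.4.2 and 6.4.5.
- Reword the parenthetical in 6.4.1 so that the SAE abbreviation no longer labels the 24-hour trigger.
- Record relatedness and expectedness as separate attributes of every SAE, and let them govern only expedited reporting under 6.4.1, 6.4.2 and 6.4.6.
- When making this change, check that the case report form sentence in 6.4.5 captures every SAE, whatever its attribution.

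The cost is protocol wording and possibly a few more SAEs in the routine reports. Expedited reporting is largely unchanged, because those rules already carry their own relatedness conditions. No visit, dose or sample size changes.
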